## **8.2 Background Characteristics**

### **8.2.1 Subject Disposition**

A disposition table will be provided for the Run-in Period with the following categories:

- All Subjects Set
- Safety Set for the Run-in Period

The number and percentage (based on the Safety Set for the Run-in Period) of subjects in each of the following disposition categories will be summarized:

- Completed Run-in Period treatment
- Prematurely discontinued Run-in Period treatment and the reason for treatment discontinuation
- Prematurely discontinued study in the Run-in Period and the reason for study discontinuation

A separate disposition table will be provided for the Treatment Period with the following categories:

- Randomized
- Safety Set for the Treatment Period
- Full Analysis Set (FAS)
- Randomized but not dosed

The number and percentage (based on the FAS) of subjects in each of the following disposition categories will be summarized by treatment group and overall:

- Completed treatment
- Prematurely discontinued treatment and the reason for discontinuation
- Completed study
- Prematurely discontinued study and the reason for discontinuation
- Rollover to open-label extension study

A listing will be provided for subjects who discontinued treatment (including both the Run-in Period and the Treatment Period) or who discontinued study with reasons for discontinuation.

### **8.2.2 Demographics and Baseline Characteristics**

Demographics and baseline characteristics will be summarized by treatment group and overall based on the FAS.

Demographic data will include the following:

- Age at Day 1 (in years)
- Sex (male; female)
- Ethnicity (Hispanic or Latino; Not Hispanic or Latino; Not Collected per Local Regulations)
- Race (White; Black or African American; Northeast Asian; Southeast Asian; Other Asian; Asian (Region Not Reported); American Indian or Alaska Native; Native Hawaiian or Other Pacific Islander; Other; Multiracial; Not Collected per Local Regulations)
- Geographic region (North America [including United States and Canada]; Rest of the World [including Europe, Israel, Australia, and New Zealand])

Baseline characteristics will include the following:

- Weight (kg)
- Height (cm)
- BMI (kg/m^2)
- BMI z-score (for subjects  $\leq 20$  years old at Baseline)

Stratification categories will include the following:

- Age at the Screening Visit (<18;  $\geq 18$  years)

- ppFEV1 at Day -14 (<70; ≥70 percentage points)
- SwCl at Day -14 (<30; ≥30 mmol/L)
- Prior CFTR modulator Use (Yes; No)
- Genotype group (F/F, F/G, F/RF, TCR/non-F)

Disease characteristics will include the following:

- ppFEV1 at baseline (<40; ≥ 40 to <70; ≥70 to ≤90; >90 percentage points)
- ppFEV1 at baseline (continuous)
- Sweat chloride at baseline (<30; ≥30 to <60; ≥60 mmol/L)
- Sweat chloride at baseline (continuous)
- CFQ-R respiratory domain score at baseline (adult and child version only) (continuous)
- Prior use of dornase alfa before first dose of study drug in the Treatment Period (Yes; No)
- Prior use of azithromycin before first dose of study drug in the Treatment Period (Yes; No)
- Prior use of inhaled antibiotic before first dose of study drug in the Treatment Period (Yes; No)
- Prior use of any bronchodilator before first dose of study drug in the Treatment Period (Yes; No)
- Prior use of inhaled hypertonic saline before first dose of study drug in the Treatment Period (Yes; No)
- Infection with *Pseudomonas aeruginosa* within 2 years prior to screening (Positive; Negative)

In addition, data listings will also be provided for:

- Informed consent
- Inclusion/exclusion criteria violation for subjects with any such violations

### **8.2.3 Medical History**

Medical history will be coded using the Medical Dictionary for Regulatory Activities (MedDRA). For the FAS, medical history will be summarized descriptively by System Organ Class (SOC) and Preferred Term (PT). This summary will be provided by treatment group and overall. The corresponding data listing will also be provided.

In addition, the number of subjects reported to have had positive cultures for respiratory pathogens within the 2 years prior to screening (i.e., answered yes on the respiratory microbiology form) will be summarized by treatment group and overall for the FAS. The corresponding data listing will be provided.

### **8.2.4 Prior and Concomitant Medications**

Medications will be coded using the World Health Organization Drug Dictionary (WHODrug) and categorized as follows:

**Prior medication:** any medication that was administered during the 56 days before the first dose of study drug in the Treatment Period excluding the ones that started in the Run-in Period. For subjects who discontinue during the Run-in Period and whose first dose of study drug in the Treatment Period is not available, prior medication will be any medication that was administered during the 56 days before the last dose of study drug in the Run-in Period excluding the ones that started after the first dose in the Run-in Period.

**Concomitant medication during the Run-in Period:** medication continued or newly received during the TE Period for the Run-in Period

**Concomitant medication during the Treatment Period:** medication continued or newly received during the TE Period for the Treatment Period

**Post-treatment medication:** medication continued or newly received after:

- the TE Period for the Run-in Period if the subject did not receive study drug in the Treatment Period
- the TE Period for the Treatment Period for subjects who received study drug in the Treatment Period

A given medication may be classified as any combination of the above categories: for example, prior and concomitant during the Run-in Period, concomitant during the Treatment Period and post-treatment, or concomitant for both periods and post-treatment.

If a medication has a completely missing or partially missing start/stop date and if it cannot be determined whether it was taken before the first dose date of study drug, concomitantly, or after the TE Period, it will be classified as prior, concomitant for both periods, and post-treatment. Details for imputing missing or partial start and/or stop dates of medication are described in [Appendix](#).

Prior medications and concomitant medications will be summarized descriptively for the FAS using frequency tables by: 1) treatment group and overall, Preferred Name (PN); and 2) treatment group and overall, Anatomical Therapeutic Chemical class (ATC) level 1, ATC level 2, and PN.

Prior medications and concomitant medications during the Run-in Period will be summarized together in one summary table. Post-treatment medications will be listed in the all medications listing.

### **8.2.5 Study Drug Exposure**

Study drug exposure will be summarized by treatment group and overall for the Treatment Period only based on the Safety Set for the Treatment Period.

Duration of study drug exposure (in days) will be calculated as: last dose date of study drug during the Treatment Period – first dose date of study drug during the Treatment Period + 1, regardless of study drug interruption.

Study drug exposure (in weeks) will be summarized descriptively by the number of subjects (n), mean, SD, median, min, and max. It will also be summarized by interval ( $\leq 1$  week;  $>1$  to  $\leq 2$  weeks;  $>2$  to  $\leq 4$  weeks;  $>4$  to  $\leq 12$  weeks;  $>12$  to  $\leq 24$  weeks;  $>24$  to  $\leq 36$  weeks;  $>36$  to  $\leq 52$  weeks;  $>52$  weeks) using counts and percentages. Additionally, the total study drug exposure,

defined as the sum total of the study drug exposure across all subjects (in patient-weeks and patient-years), will be provided.

### **8.2.6 Study Drug Compliance**

Study drug compliance will be summarized by treatment group and overall for the Treatment Period only based on the FAS.

Study drug compliance will be calculated as:  $100 \times [1 - (\text{total number of days of study drug interruption during the Treatment Period}) / (\text{duration of study drug exposure in days during the Treatment Period})]$ . A study drug interruption on a given day is defined as an interruption of any study drug on that day.

Percentage of study drug compliance will be summarized descriptively by the number of subjects (n), mean, SD, median, min, and max. It will also be summarized in categories (<80%; ≥80%) using frequency tables.

### **8.2.7 Important Protocol Deviations**

An important protocol deviation (IPD) is a deviation that may significantly impact the completeness, accuracy, or reliability of key study data or that may significantly affect a subject's rights, safety or well-being. IPDs will be identified by the PD review team according to the protocol deviation plan which will be finalized before the database lock.

IPDs will be summarized descriptively based on the FAS and presented by treatment group and overall. Additionally, IPDs will be provided in an individual subject data listing.

## **8.3 Efficacy Analysis**

All efficacy analyses described in this section will be based on the FAS, unless otherwise specified. The analysis of the below secondary endpoints will be performed based on the PFAS in order to increase the power for the analyses:

- Proportion of subjects with SwCl <60 mmol/L through Week 24 (pooled with data from Study 102)
- Proportion of subjects with SwCl <30 mmol/L through Week 24 (pooled with data from Study 102)

The primary and key secondary endpoints will be formally tested for statistical significance, and the tests will be subject to multiplicity control (see 8.3.2.3 for details). The endpoints involving ppFEV1 and SwCl which are not primary or key secondary will be supportive and analyzed similarly to the corresponding primary and key secondary endpoints; the *P* value presented will be nominal.

### **8.3.1 Analysis of Primary Efficacy Variable**

#### **8.3.1.1 Definition of Primary Efficacy Variable**

The primary efficacy variable is the absolute change from baseline in ppFEV1 through Week 24 (estimated by averaging Weeks 16 and 24). Percent predicted FEV1 is the ratio of observed FEV1 (L) and predicted FEV1 (L), expressed as a percentage. See [Appendix](#) for more details.

#### **8.3.1.2 Definition of Primary Estimand**

The primary estimand is defined as the following and is presented in [Appendix](#) :

- Treatment: VNZ/TEZ/D-IVA versus ELX/TEZ/IVA
- Population: Study population represented by inclusion and exclusion criteria
- Variable: Absolute change from baseline (after ELX/TEZ/IVA run-in) in ppFEV1 through Week 24 (estimated by averaging Weeks 16 and 24)
- Handling of intercurrent events (ICE):
  - o The treatment policy strategy will be used to handle the use of non-study drug CFTR modulators for >3 days in either the Run-in Period or the Treatment Period prior to Week 24, which means that observed ppFEV1 values will be used, if available, after this prohibited medication use.
  - o The treatment policy strategy will be used to handle treatment discontinuation prior to Week 24, which means that observed ppFEV1 values will be used, if available, after treatment discontinuation.
- Population level summary: Difference in variable means between VNZ/TEZ/D-IVA and ELX/TEZ/IVA groups

### 8.3.1.3 Primary Analysis

The primary null hypothesis to be tested is that the mean for the primary efficacy variable for VNZ/TEZ/D-IVA is inferior by >3 percentage points compared to ELX/TEZ/IVA. The primary analysis of the primary estimand will be performed using a mixed-effects model for repeated measures (MMRM) with change from baseline at Day 15, Week 4, Week 8, Week 16, and Week 24 as the dependent variable. The model will include fixed categorical effects for treatment, visit, age at screening (<18 versus ≥18 years of age), genotype group (F/F, F/G, F/RF, TCR/non-F), and treatment-by-visit interaction, with baseline ppFEV1 and baseline SwCl as continuous covariates. The model will be estimated using restricted maximum likelihood. Denominator degrees of freedom for the *F*-test for fixed effects will be estimated using the Kenward-Roger approximation. An unstructured covariance structure will be used to model the within-subject errors. If the model estimation does not converge, genotype group will be considered with two levels (F/F and non-F/F) or removed from the model, and if non-convergence persists, an alternative covariance structure like compound symmetry will be used. Conditional on the observed data and covariates, missing data will be assumed to be missing at random (MAR).

The primary result obtained from the model will be the estimated treatment difference through Week 24 (estimated by averaging Weeks 16 and 24). The adjusted mean with a 2-sided 95% CI and the 1-sided *P* value for non-inferiority will be provided. The primary null hypothesis will be rejected, and non-inferiority demonstrated, if the lower bound of the CI is ≥-3.0.

The primary null hypothesis of non-inferiority described above will be tested based on the FAS.

If non-inferiority for the primary endpoint is demonstrated, and if the lower bound of the same 95% CI is greater than 0, then superiority for the primary endpoint is also demonstrated, and the 2-sided *P* value for superiority will be presented.

The estimated within-group change from baseline and treatment difference at each post-baseline visit, obtained from the model, will be provided. The estimated within-group change and its standard error (SE) at each post-baseline visit will also be plotted by treatment group.

### 8.3.1.4 Supplementary Analysis

#### 8.3.1.4.1 Alternative Estimand using Hypothetical Strategy

An alternative estimand will be defined similarly to the primary estimand with the exception that ICE will be addressed using the hypothetical strategy. In the hypothetical strategy, observed values after ICE will be set to missing to provide a conservative and robust test of non-inferiority for the primary endpoint. Supplementary analysis of this alternative estimand will be performed similarly to the primary analysis as specified in 8.3.1.3. Additional details are presented in [Appendix](#) .

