##### **9.1.5.2 Discontinuation During the Treatment Period**

Subjects who prematurely discontinue study drug treatment during the Treatment Period should continue to complete all scheduled study visits for assessments following completion of the ETT Visit (and Safety Follow-up Visit, if applicable), as detailed in Table 3-2.

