## 6.2 Sample Size and Power

### 6.2.1 Power for Primary Analysis of Primary Efficacy Endpoint

The primary efficacy endpoint is the absolute change from baseline in ppFEV1 through Week 24. The primary null hypothesis to be tested is that the mean absolute change in ppFEV1 from baseline through Week 24 for VNZ/TEZ/D-IVA is inferior by >3 percentage points compared to ELX/TEZ/IVA.

The non-inferiority margin represents a clinically acceptable loss of effectiveness as outlined in regulatory guidances. Furthermore, a statistical approach using the Rothmann method recommends that the non-inferiority margin preserve at least 50% of the treatment effect of the active control (ELX/TEZ/IVA) compared to placebo, where the treatment effect is estimated by the lower bound of the 95% confidence interval (CI). In the overall population eligible for this

study, the lower bound of the 95% CI of the treatment effect for ELX/TEZ/IVA is approximately 12 percentage points for ppFEV1. The selected non-inferiority margin of 3 percentage points is consistent with this statistical method and the non-inferiority margin for ppFEV1 used in clinical studies evaluating symptomatic CF treatments.

The null hypothesis will be tested at a 1-sided significance level of 0.025.

Assuming a within-group standard deviation (SD) of 8 and a 10% drop-out rate at Week 24 and a treatment difference of 0 between VNZ/TEZ/D-IVA and ELX/TEZ/IVA, a sample size of 275 subjects in each group for a total of 550 subjects will have more than 95% power to test the primary hypothesis for the primary endpoint, based on a 1-sided, 2-sample *t*-test at a significance level of 0.025.

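### SAP 8.3.1.4.1 calls the hypothetical-strategy refit conservative without condition; for subjects who stop study drug and take no other modulator, it can be the more lenient non-inferiority analysis

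*SAP*

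**What the plan says.** The primary estimand (SAP 8.3.1.2) names two intercurrent events: stopping study drug before Week 24, and more than 3 days of a non-study CFTR modulator. Values observed after either event are kept. For stopping, "The treatment policy strategy will be used to handle treatment discontinuation prior to Week 24". Such values are planned for: Protocol 9.1.5.2 states that "Subjects who prematurely discontinue study drug treatment during the Treatment Period should continue to complete all scheduled study visits".

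SAP 8.3.1.4.1 then defines the one supplementary analysis of the primary endpoint. In it, "observed values after ICE will be set to missing to provide a conservative and robust test of non-inferiority for the primary endpoint". No condition or supporting argument follows. Appendix D applies this single rule to both events, and the refit uses the MMRM of SAP 8.3.1.3, which assumes missing at random.

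SAP 6.2.1 gives the scale. The null hypothesis is that VNZ/TEZ/D-IVA (VX-121/TEZ/D-IVA in the protocol) is "inferior by >3 percentage points compared to ELX/TEZ/IVA", and "the lower bound of the 95% CI of the treatment effect for ELX/TEZ/IVA is approximately 12 percentage points" when compared with placebo.

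**The concern.** One deletion rule covers two events that can move the treatment difference in opposite directions.

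- **Non-study modulator use.** If the replacement brings subjects close to the control regimen, values observed afterwards make the arms alike. Deleting them removes dilution of a true deficit, which is conservative.
- **Stopping without a replacement modulator.** Baseline is measured on ELX/TEZ/IVA, so loss after stopping appears as a negative change. The primary analysis counts it. The refit deletes it and models the subject as if still on drug. If this happens more often on VNZ/TEZ/D-IVA, deletion favours VNZ/TEZ/D-IVA.

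Balance between arms cannot be presumed. Under Protocol 9.1.2 and 9.1.5.1, subjects who discontinue during the ELX/TEZ/IVA run-in are not randomised. The trial therefore selects for short-term tolerance of the control, with no equivalent filter for the new regimen. This does not show that an imbalance will occur.

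Little else supports a robustness statement. Protocol 12.2 leaves the details of a per-protocol set to the SAP, and SAP section 7 defines none. Protocol 12.3.3.1 leaves missing-data sensitivity analyses to the SAP, and the SAP has none for the primary endpoint that departs from missing at random. If the refit agrees with the primary analysis, the SAP's label invites readers to treat it as having passed a stricter test.

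**Working it through.** **Inputs from SAP 6.2.1.** Margin 3 points; 1-sided alpha 0.025; SD 8; 275 per arm; 10% drop-out; control effect about 12 points versus placebo (lower 95% bound).

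**The plan's own figure.** Evaluable per arm = 275 x 0.9 = 247.5. SE = 8 x sqrt(2/247.5) = 0.719. Power at a true difference of 0 = Phi(3/0.719 - 1.96) = 98.6%, which agrees with the stated figure of more than 95%. The 95% CI half-width is 1.96 x 0.719 = 1.41.

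**Assumptions not in the documents.**
- pT and pC: proportions stopping on VNZ/TEZ/D-IVA and on ELX/TEZ/IVA, 5% to 15%.
- L: off-drug level in points below baseline, the same in both arms. L = 12 borrows the control effect as an upper scenario; 6 and 3 are lower ones. L = 0 stands for stoppers who all move to the control regimen.
- d: on-drug difference, VNZ/TEZ/D-IVA minus ELX/TEZ/IVA, with on-drug change on control taken as 0.
- Stoppers are off drug at both Week 16 and Week 24, and attend.

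**Direction.**
- Treatment policy: TP = (1 - pT)d - L(pT - pC).
- Hypothetical, under missing at random: HYP = d.
- HYP - TP = pT(d + L) - pC x L.

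The refit gives the more favourable estimate when pT(d + L) > pC x L. With equal stopping the gap is pT x d, and with L = 0 it is also pT x d; both are negative when d is negative, so the refit is then stricter.

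For d = -1.5 and pC = 5%, the refit becomes the more lenient once pT exceeds pC x L/(d + L):
- L = 12: 0.05 x 12/10.5 = 5.7%
- L = 6: 0.05 x 6/4.5 = 6.7%
- L = 3: 0.05 x 3/1.5 = 10%

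**Size of the gap.** At d = 0, L = 12 and 15%/5% stopping, TP = -12 x 0.10 = -1.20 and HYP = 0. The gap of 1.2 is 40% of the margin. At L = 3 it is 0.3. A simulation of the L = 12 case (1,500 replicates, five visits, assumed correlation 0.6) gave mean estimates of -1.21 and -0.01.

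**Refit when the treatment-policy difference is exactly -3.** Solve d = (-3 + L(pT - pC))/(1 - pT). The chance that the refit's lower bound is at or above -3.0 is Phi((d + 3)/0.719 - 1.96). The primary analysis would pass 2.5% of the time here.

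| Stopping VNZ / ELX | L | d | Refit bound at or above -3.0 |
|---|---|---|---|
| 10% / 5% | 12 | -2.67 | 7% |
| 15% / 5% | 12 | -2.12 | 23% |
| 10% / 5% | 6 | -3.00 | 2.5% |
| 15% / 5% | 6 | -2.82 | 4% |
| 10% / 5% | 3 | -3.17 | 1.4% |
| 15% / 5% | 3 | -3.18 | 1.4% |
| 10% / 10% | any | -3.33 | 0.8% |
| 15% / 5% | 0 | -3.53 | 0.35% |

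Rows above 2.5% are those where the refit is the more lenient. The last four rows are those where it is stricter.

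**Can the two analyses disagree?** Take d = -1, stopping 8%/2% and L = 12. TP = -0.92 - 0.72 = -1.64, with lower bound -1.64 - 1.41 = -3.05 (fail). HYP = -1, with lower bound -2.41 (pass). The example is borderline: with L = 11 the treatment-policy bound is -2.99, and at 15%/9% with L = 12 it is -2.98, so both analyses pass.

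**The case against.** The strongest reply is that the supplementary analysis decides nothing. SAP 8.3.1.3 rejects the null only on the treatment-policy MMRM in the FAS. Where stoppers on the new regimen lose function off drug, that primary analysis is already the stricter one; where a deficit is diluted, the refit is stricter. If both pass, the penalty for stopping has been paid in the primary analysis. All of this stands, and it limits the consequence to interpretation.

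Stoppers may also take another modulator. Protocol Table 9-2 bars Vertex CFTR modulators only until after the last dose of study drug. For those subjects L may be near 0 and the SAP's wording is then sound. This also stands. The SAP reports discontinuation with reasons by arm (8.2.1) and concomitant medication by arm (8.2.4). But medication starting after the treatment-emergent period is only listed, so modulator use after stopping would be tabulated only in part.

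Three stronger readings are tempting, and the documents do not support them:

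- A reader might infer that the trial's type I error is inflated. It is not: the percentages in the table describe a supplementary analysis of a different estimand, with no decision rule attached.
- A reader might infer that the refit passes more easily whenever the new drug is stopped more often. The L = 3 rows show the reverse.
- A reader might take 12 points off the VNZ/TEZ/D-IVA on-drug mean and obtain 13% and 39% for 5- and 10-point excesses. That leaves subjects carrying the new drug's on-drug deficit after they have stopped it. With a common untreated level the figures are 7% and 23%.

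Finally, 12 points is an effect versus placebo, not a measured loss after stopping, and a 10-point excess is large beside a planned 10% drop-out. These are upper scenarios.

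**Conclusion.** The unconditional label is not correct. Whether the refit is conservative depends on stopping by arm, the loss after stopping and what stoppers take next; the documents give none of these. With a true on-drug deficit, the label is right for values after non-study modulator use, provided that the replacement brings subjects near the control regimen. It is also right when stopping is balanced or higher on control. It fails for discontinuation without a replacement modulator once pT(d + L) exceeds pC x L.

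Under the stated assumptions the effect runs from material (23% against 2.5% at L = 12 and 15%/5% stopping) to absent or reversed (1.4% at L = 3). The primary test is unaffected. What is at stake is false reassurance from the only supplementary analysis of the primary endpoint, which justifies a change to the SAP but does not cast doubt on the primary analysis.

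**What to change.** 1. In SAP 8.3.1.4.1, delete the claim that the test is conservative and robust, or state the conditions under which it holds.
2. In 8.3.1.4.1 and Appendix D, add one run of the same MMRM with a separate strategy per event. Keep observed values after treatment discontinuation until non-study CFTR modulator use exceeds 3 days, and set only later values to missing. State that modulator use after the last study dose counts, since Table 9-2 no longer prohibits Vertex modulators at that point.
3. Keep the planned refit. Report the primary result, the planned refit and the new run together, with discontinuation and post-discontinuation modulator use by arm.

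No new formal rule for declaring robustness is needed. The cost is SAP wording and one more run of an existing model. The event types and dates are already required for Appendix D, and no visit, data item or primary test changes. The downside is that the robustness statement may become less favourable.
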